B2.1. PTSD, Cognitive Deficit, and ADHD: In our on-going project, we evaluated combat veterans with and without PTSD with Clinician Administered PTSD Scale (CAPS), Conners' Adult ADHD Rating Scales–Self Report: Short Version (CAARS–S:S, score > 65 is regarded clinical significant cognitive impairment; Conner et al 1999). We included 47 participants, 29 PTSD subject (13 with CAARS > 65, 45%) and 18 controls (2 with SAARS > 65, 11%). The results indicated PTSD diagnosis is associated with significantly higher self-reported attentional and executive dysfunction symptoms ($\chi^2 = 5.81, p = 0.16$). This was also evident in the significant correlations between CAPS and CAARS-S:S scores ($R=0.497, p < 0.01$), and CAPS PTSD symptoms ($\beta=.26, t=1.88, p=.05$), and PTSD patient cognitive deficit severity as measured by the CAARS-S:S ($\beta=.59, t=4.81, p<.001, R^2=.34$). These findings further support available literature suggesting that cognitive symptoms associated with PTSD diagnosis are highly correlated with patients' functional outcome.

B2.2. MPH Improves Cognitive Function: Further, we conducted additional preliminary analyses with 8 PTSD individuals with cognitive symptoms who were treated with MPH. Analyses conducted on clinical assessments of patients' PTSD and ADHD symptoms (CAPS and CAARS-S:S) before and after MPH treatment revealed significant reductions in both PTSD and self-reported cognitive deficit symptoms (see Fig1 and Fig2; $F(1, 7) = 22.39, p = .002$).

C. RESEARCH DESIGN AND METHODS:

C1. Overview: The proposed project is a pilot, feasibility double-blind crossover study to investigate the efficacy and safety of ATX with comorbid PTSD/ADHD patients to reduce cognitive symptoms, improve treatment retention and response, and improve patient's activities of daily living. A prospective, 10-week, fixed-dose, randomized, double-blind, placebo-controlled, and cross-over trial of ATX as an adjunctive medication to other therapies will be conducted among veterans with comorbid PTSD/ADHD. The short-duration, crossover design, and blind enable the study to be feasible in both time and funding level. **The Primary Objective** is to assess the efficacy of fixed dose of ATX (80mg) (compared with placebo) in reducing cognitive symptoms in comorbid ADHD/PTSD such that functional

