impairment and treatment retention are both improved, while **The Secondary Objective** is to replicate the our preliminary finding of negative impact of cognitive symptoms of ADHD on PTSD clinical outcomes. **The Tertiary Objective** is to assess the efficacy of ATX in reducing broad spectrum of PTSD symptoms. The proposed study will take 10 weeks and include two phases (**Phase I**: Initial Phase, 5 weeks; **Phase II**: Crossover Phase, 5 weeks). The crossover design was employed to both achieve study objectives while minimizing costs. Each phase consists two periods: **Period I** (week1 in Phase I and week6 in phase II) consist of psychological and physical assessments and placebo lead-in/wash-out, in which subjects take 6 days placebo; **Period II** (weeks 2-5 in Phase I and week7-10 in Phase II) consist of treatment with either atomoxetine 80mg daily or placebo daily). This project will take advantage of established on-going PTSD assessment and treatment clinical trials currently performed at the Ralph H. Johnson VA Medical Center (RHJVAMC) to facilitate recruitment. The proposed 50 veterans with ADHD/PTSD will be recruited from these on-going trials enabling both comprehensive assessment and evaluation of patients' engagement in ongoing PTSD treatments. Subjects will be randomized and assigned by the study investigator ([name]) into crossover group 1 (ATX at Phase I, then placebo at Phase II) or 2 (placebo at Phase I, then ATX at Phase II) with both placebo and medication administered through pharmacy. Subjects and other investigators are thus able to remain blinded to the order of treatment assignment throughout the study. The 1-week interval was based on published pharmacokinetic data for 4 week doses of ATX (*Witcher et al, 2003*). After crossover, patients will be unblinded and data will be cleaned and analyzed. Final follow up will be 30-days after last visit.

C2. Investigational Agent: ATX is a non-stimulant, FDA approved agent for treatment of ADHD. ATX 80mg is the most common adult dose used in ADHD with and without comorbid condition (Adler et al, 2009). In this project, 80 mg ATX and placebo will be prepared in capsules with identical appearance and similar taste by Eli Lilly and Company, Indianapolis, Indiana.

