Inclusion Criteria: 1) OIF/OEF Veterans age 20 to 60 with PTSD and significant ADHD symptoms (CAARS-S:S > 65); 2) Good physical health. 3) Trauma exposure sufficient to meet Category A of PTSD criteria (Breslau and Kessler 2001)

Exclusion Criteria: 1) Age younger than 20 or greater than 60. 2) Known sensitivity to ATX. 3) Presence of disorders that could conceivably be exacerbated by atomoxetine (specifically, narrow

angle closure glaucoma, urinary outflow obstruction, hypertension, and neurological disorders, particularly tics and Tourette's syndrome, or a history of epilepsy or seizures). 4) use of concomitant medication that could potentially interact with atomoxetine including monoamine oxidase inhibitors (MAOI), antihypertensive medication, or any concomitant medication that was a cytochrome 2D6 inhibitor (CYP2D6) as atomoxetine's elimination involves the CYP2D6 system. 5) An active or lifetime major mental health diagnosis as determined by DSM-IV Axis I Disorders, including schizophrenia, schizoaffective disorder, psychotic disorder not otherwise specified, bipolar I disorder, bipolar II disorder, bipolar disorder not otherwise specified. The project will allow presence of depressive disorders if the depressive episodes are secondary to PTSD. 6) Current substance dependence and abuse (within 3 month). 7) Females who are pregnant or likely to become pregnant. 8) Active suicidal thoughts and behavior.

Suicide Screen: A screen for recent or current suicidal thought and/or attempts will be conducted before the interview. If a subject reports suicidal thought at the time of interview, his physician or psychiatrist will be informed and the subject will be escorted to the ER immediately for further evaluation and treatment.

Screening/Baseline Evaluation: During this visit subjects will review and sign the Informed Consent. Eligibility to participate in this portion of the study will be determined by a minimum 6-month duration of PTSD illness, CAARS-S:S score of 65 or higher as well as a positive ADHD score for the adult section of the Conners ADHD interview, a total CAPS severity score of 55 or higher at the baseline visit. If the subjects qualify, then a medical/psychiatric history will be obtained along with laboratory safety measures, including electrocardiogram (EKG), liver and renal panel (SMA-12), complete blood count with differential, urine toxicology screen and concomitant meds. If the veteran is female, urine pregnancy test will be obtained.

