Concom meds	X	X	X		X	X		
AEs			X			X		

Safety assessments: At each study visit, safety will be assessed by measuring: weight, sitting blood pressure, heart rate, adverse events (except baseline), and use of concomitant medications. Laboratory and EKG assessments will be performed at baseline, one and seven weeks. Anxiety, depression, and suicidal ideation will be assessed with Ham-A, Ham-D, and suicide screen in each of the visits. Compliance will be assessed by pill counts and appointment attendance. Referrals to the Charleston PTSD clinic will be conducted at the final study visit for any remaining PTSD symptoms and the CBT clinic for remaining ADHD symptoms.

Follow-up: The final visit, 30-days after study completion, will include safety assessments, along with follow-up of any unresolved adverse events. This visit will also provide assurance that veterans who participated in this medication study will have adequate follow-up care in the Charleston VAMC PTSD or Mental Health Outpatient Clinic either with continued medication or psychotherapy. This visit may be done over the phone or by mail.

Diagnostic Procedures: After obtaining the informed consent, a trained research assistant will perform the initial interview and administer all of the diagnostic scales to the participants. [name], [name] (MD, Co-Investigator) and [name] (PI) will make the final diagnosis based on all the data collected. The DSM-IV diagnostic criteria will be used to ascertain each phenotype.

Database Management: All collected clinical, demographic, and geographic data will be stored in Research Database Storage in the Charleston VAMC PTSD Program. The genotyping data will be stored in [name] laboratory Research Database. For each patient, the clinical database will provide information as following: age, gender, ethnic origin, medical and psychiatric diagnosis, family history, developmental history, and existence of comorbidity. The genotyping data will be separately entered without knowledge of clinical data. Strict confidentiality is maintained regarding database information, which is secured and for research purposes only. All the specimens from the subjects will be labeled by code at the clinic. Names will not appear on specimens, nor will they be available in the laboratory. The person conducting the genotyping is blind to the clinical profile of the subject. No names or identifiable information will be used in any data presentation.

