Statistical Analyses and Power Estimation: As a pilot feasibility study with double-blind crossover design, the design affords greater power and need for enrollment of fewer subjects. Similar design with this medication has suggested sample size of 40 was sufficient for effect sizes typically observed with this medication in similar populations (Bain et al 2013). To account for patient dropouts, the study will enroll/consent up to 50 patients. This will ensure 40 subjects complete the entire study. This design will allow initial pilot feasibility data, improved control and testing of causation, and greater power in the allotted time-frame and funding level. The primary consideration is difference in outcome between baseline and endpoint with ATX treatment as compared to placebo. The primary outcome measure a priori will be the change in total CAARS-S:S scores, AAQoL-29 and BAARS-IV. Secondary measures include the remaining efficacy and safety measures as delineated above. The primary outcome of interest is the moderating impact of ATX treatment (medication \times ADHD TAU) on treatment response (pre- and post-treatment measures of cognitive symptoms of ADHD and PTSD, functional impairment in daily living domains, and global functioning). A mixed model, repeated-measures multivariate analysis of variance with pre- and post-ADHD TAU treatment ADHD symptoms, functioning, and global functioning entered as repeated measures; and ATX treatment entered as the between factors. Pre-treatment PTSD severity scores (CAPS) will also be entered into the model as a potential explanatory covariate. Simple slopes using repeated measures ANOVA will be used to probe significant interactions

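### Post-baseline labs and EKG fall no later than day 7–8 of the 28 days on atomoxetine, and Table 1 and the safety text disagree on test weeks and adverse-event visits

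*Combined protocol and SAP*

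**What the plan says.** **Treatment calendar.** C1 (Overview) splits each five-week phase into a one-week Period I, described as "placebo lead-in/wash-out, in which subjects take 6 days placebo", and a four-week Period II: "weeks 2-5 in Phase I and week7-10 in Phase II) consist of treatment with either atomoxetine 80mg daily or placebo daily". Group 1 takes ATX in Phase I and placebo in Phase II; group 2 the reverse.

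**Labs and EKG.** The Safety assessments paragraph in C3 reads "Laboratory and EKG assessments will be performed at baseline, one and seven weeks". Table 1 ticks the lab/EKG row at Screening/Baseline, W2 and W7, and leaves W1, W5, W6, W10 and W14 blank.

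**Adverse events.** The same paragraph lists what is measured at every study visit, including "adverse events (except baseline), and use of concomitant medications". Table 1 ticks the adverse-event row at W2 and W7 only.

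**Role of safety.** C1 describes the study as one "to investigate the efficacy and safety of ATX with comorbid PTSD/ADHD patients". The Statistical Analyses and Power Estimation section adds: "Secondary measures include the remaining efficacy and safety measures as delineated above".

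**The concern.** Labs and EKG are the only scheduled assessments that can show a liver or QT effect of ATX. The plan's own list of serious adverse effects (section 1.1c) includes severe liver injury, liver failure and QT prolongation, and gives no time of onset. A result from the first week on drug therefore cannot be taken to speak for the remaining three weeks. The exclusions and the baseline EKG and liver panel lower the risk at entry, but they do not measure what happens on treatment. With the present schedule, the trial cannot report labs or EKG at the end of either treatment period.

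The two conflicts add a practical problem. Staff have two sets of lab/EKG weeks to choose from, and one of them gives half the design no on-drug test. They also have two adverse-event schedules. Anyone working from Table 1 alone would first ask group 1 about weeks 3–5 at W7, after washout, and would have no ticked visit for group 2's weeks 8–10.

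**Working it through.** **Inputs.** Placebo in weeks 1 and 6 and treatment in weeks 2–5 and 7–10 (C1); visit weeks and ticks (Table 1); text schedule (C3, Safety assessments). The plan does not say where in its week a visit falls, so both ends are shown. Assumption: week k covers study days 7(k−1)+1 to 7k.

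**Reproducing the plan's duration.** 2 × (1 + 4) = 10 weeks, as stated. Treatment is 4 × 7 = 28 days per phase.

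**Check on the table columns.** The CGI-I row, read the same way, gives W2, W5, W6, W7 and W10. That matches the C3 text, which excludes only baseline and W1 among the study visits, apart from the W14 follow-up. The column reading is secure.

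**Step 1: ATX day of the on-drug test under Table 1.** ATX day = visit day − first ATX day + 1. The first ATX day is 8 or 43 after a full lead-in week, and 7 or 42 after a strict six-day lead-in.

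| Group | Visit | First ATX day | Visit opens its week | Visit closes its week |
|---|---|---|---|---|
| 1 | W2 (days 8–14) | 8 | 8 − 8 + 1 = 1 | 14 − 8 + 1 = 7 |
| 1 | W2 | 7 | 8 − 7 + 1 = 2 | 14 − 7 + 1 = 8 |
| 2 | W7 (days 43–49) | 43 | 43 − 43 + 1 = 1 | 49 − 43 + 1 = 7 |
| 2 | W7 | 42 | 43 − 42 + 1 = 2 | 49 − 42 + 1 = 8 |

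The other post-baseline set is never on ATX. Group 1's W7 falls 43 − 35 = 8 to 49 − 35 = 14 days after its ATX phase ended, and group 2's W2 precedes ATX.

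Days of a 28-day course after the latest possible test: 28 − 7 = 21 (75%) or 28 − 8 = 20 (71%). Table 1 ticks dispensing at W1, W2, W6 and W7, which suggests that lead-in capsules are handed out at W1 and W6 and treatment capsules at W2 and W7. If so, the W2 and W7 tests precede or coincide with the first dose, and all 28 days lack an on-drug test.

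**Step 2: the text read literally.** Week 1 is placebo lead-in for both groups (with a strict six-day lead-in, its last day could at most be ATX day 1). Week 7 is placebo for group 1. So group 1 has essentially no on-drug test, and group 2 has one by day 7–8.

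**Step 3: can one way of counting weeks reconcile text and table?** Count elapsed weeks from study start. If visits open their weeks, one elapsed week is W2, but seven elapsed weeks is the start of week 8, where there is no visit. If visits close their weeks, seven elapsed weeks is W7, but one elapsed week is W1. Neither gives W2 and W7 together.

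**Step 4: adverse-event visits.** Text: W1, W2, W5, W6, W7, W10, W14 = 7. Table 1: W2, W7 = 2.

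**Step 5: ATX day if the sets move to W5 (days 29–35) and W10 (days 64–70).**
- Visits open their weeks: 29 − 8 + 1 = 22 or 29 − 7 + 1 = 23; for W10, 64 − 43 + 1 = 22 or 64 − 42 + 1 = 23.
- Visits close their weeks: 35 − 8 + 1 = 28 or 35 − 7 + 1 = 29; for W10, 70 − 43 + 1 = 28 or 70 − 42 + 1 = 29. (Day 29 arises only if a strict six-day lead-in is followed by dosing to the end of the phase.)

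**The case against.** **Late ATX is not unmonitored.** Table 1 ticks vital signs at every visit through W10. The drug is approved for ADHD and given at a common adult dose for four weeks. Hypertension, antihypertensives and CYP2D6 inhibitors are excluded, and none of the three stated objectives is a safety objective. All of this stands and limits the severity. It does not supply a late liver panel or EKG. The W14 visit does not either: it comes about 30 days after the last visit, may be by phone or mail, and has no lab/EKG tick. Section 1.5, despite its title, deals with data storage and confidentiality.

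**Adverse events are already covered.** A reader might infer from Table 1 that events go unasked for most of the ATX period. The documents do not support that: the C3 text requires them at every visit except baseline, and Table 1 is titled an outline. The table is also thinner than the text elsewhere. It leaves concomitant medications blank at W5, W10 and W14, and Ham-A and Ham-D blank at W1, although the text asks for all three at each visit. This objection stands; the adverse-event part is a table to be corrected, not a gap in planned collection.

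**An early test has its own rationale.** ATX is fixed at 80 mg with no titration described, so a first-week check is reasonable. With no onset times given, the documents cannot show that a week-5 test finds more than a week-2 test. That stands as a reason to state the trade-off and to offer adding tests as well as moving them. It does not justify having no test after the first week.

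**Conclusion.** The point holds. Under Table 1 each patient has at most one lab/EKG set on ATX, no later than day 7–8 of 28, and none if treatment is first dispensed at W2 and W7. The text conflicts with Table 1 and, read literally, gives group 1 no on-drug set. Table 1's adverse-event row contradicts the text, and the text should govern.

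The day 7–8 limit is an upper bound. It rests on the C1 calendar, on visits falling within their labelled weeks, and on a lead-in of six or seven days.

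A reader might infer that moving the tests guarantees an end-of-treatment result for each of the 40 expected completers ("This will ensure 40 subjects complete the entire study"). That follows only if visits close their weeks. If they open them, the test falls on ATX day 22–23, and about 5–6 days of a 28-day course still follow it.

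Severity is moderate to minor. The efficacy comparison and the sample size are unaffected.

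**What to change.** (a) In Table 1, move the two post-baseline lab/EKG ticks from W2 and W7 to the existing W5 and W10 visits, taken before that phase's last dose. Change the C3 sentence to baseline, week 5 and week 10. For a patient who stops early, take the set at the last visit attended on treatment.

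(b) In Table 1, tick adverse events at W1, W2, W5, W6, W7, W10 and W14, to match C3.

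**Cost.** One sentence and two table rows. There are no extra visits, and the number of lab/EKG sets per patient stays at three. The downside is that, if W2 and W7 close their weeks, the day-7 check at 80 mg is given up, although vital signs and adverse events are still recorded at those visits. A sponsor who wants that check can keep W2 and W7 and add W5 and W10. That costs two more sets per patient: 2 × 40 = 80 for the expected completers, and at most 2 × 50 = 100 for all enrolled.

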Adverse effects (AE): Typical adverse events reported significantly more frequently with atomoxetine than placebo included dry mouth, insomnia, nausea, decreased appetite, constipation, dizziness, sweating, dysuria, sexual problems and palpitations. Modest increases in heart rate and blood pressure were well tolerated and gradually decreased on cessation of treatment.

Contraindications: ATX is contraindicated in patients known to be hypersensitive to the drug and during treatment with monoamine oxidase inhibitors (hypertensive crises may result). Medication will be stored and dispensed from the Charleston VAMC investigational drug pharmacy. Records will be maintained of all doses dispensed, and Veterans will be asked to return all unused tablets and empty prescription vials to the clinic for assessment of treatment compliance.

C3. Method

Subject Recruitment: All the subjects will be recruited through Charleston VAMC Mental Health Service Line. The Charleston VAMC has a large base of potential comorbid PTSD and ADHD participants. Many clinical trials, including pharmaceutical and psychotherapeutic trials are currently conducted in conjunction with the Charleston VAMC PTSD Clinical Team (PCT) clinic and the PCT team receives numerous PTSD evaluation consults from OIF/OEF program and Primary Care. Currently the PCT clinic receives 200 to 250 new referrals yearly of OIF/OEF Veterans who meet full criteria for PTSD based on a comprehensive initial intake interview that includes CAPS and functional impairment assessments. PI, [name] currently manages pharmacological consults for OIF and OEF Veterans. A HIPAA waiver of authorization will be on file with the IRB giving the research team permission to recruit from prior study populations. Veterans with PTSD from OIF/OEF are uniquely suited for this study because statistically they have fewer confounding variables for this clinical trial, including medical conditions such as hypertension or glaucoma and cognitive impairments such as dementia. Interested veterans who participate in clinical trials are explained the nature, purpose, and procedure of the study and asked to sign an informed consent that will explain in detail the purpose of the study, potential risks and benefits of pharmacotherapy study participation and alternative treatments that may be available.

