Conners' Adult ADHD Rating Scales-Self-Report: Short Version (CAARS-S:S, Conner et al, 1999): The CAARS-S:S is a 26-item questionnaire that assesses symptoms of ADHD in persons aged ≥18 years. T-scores above 65 indicate a likelihood of moderate to severe ADHD symptoms and impairment.

The Adult ADHD Quality of Life-29 (AAQOL-29, Brod et al, 2006): AAQoL-29 is a participant-reported outcome measure used to examine disease specific functional impairments and quality of life for adults with ADHD. The AAQOL-29 includes Life Productivity, Psychological Health, Quality of Relationships, and Life Outlook subscales. Higher scores on the AAQOL-29 indicate better functioning.

The Barkley Adult ADHD Rating Scale-IV (BAARS-IV, Barkley, 2011): BAARS-IV offers an essential tool for assessing current ADHD symptoms and domains of impairment and recollections of childhood symptoms. BAARS-IV is empirically based, reliable, and valid for diagnosis and cognitive evaluation of adult ADHD.

Response Inhibition Task: The Go-NoGo (GNG) and Stop-Signal Task (SST) are classical paradigm to investigate response inhibition and response execution (higher-order motor and attention control) processing, and a reliable marker reflecting medial prefrontal functioning (Fallgatter and Strik, 1999). Further, ATX has been found to improve GNG and SST performance in ADHD patients (Nandam et al 2014; Chamberlain et al, 2007). GNG/SST require participants to implement their response to one kind of stimuli (Go/Start) and to withhold the responses to the other kind of stimuli (NoGo/Stop). Therefore, GNG commission errors SST time are a reliable marker to examine individual executive function and to measure ATX treatment response. GNG and SST will be performed at [name] TMS Laboratory.

Table 1: Outline of study procedures and assessments of the study.

Initial Assessments	Screening/ Baseline	Phase I Start	Phase I Treatment visit	Phase I Follow up, Crossover lead in	Phase II Start	Phase II Treatment visit	Phase II Follow up	Final Follow up visit
visit (week)	1	2 (W1)	3 (W2)	4 (W5)	5 (W6)	6 (W7)	7 (W10)	8 (W14)
Consent	X							
MINI	X							
CAADID Part II	X							
CES	X							
DTS	X							
CGI-S	X							
CGI-I			X	X	X	X	X	
CAARS-S:S	X	X	X	X	X	X	X	X
BAARS	X			X			X	X
AAQoL-29	X			X			X	
SF-36-V	X			X			X	
CAPS-IV	X			X			X	
Ham-D	X		X	X	X	X	X	X
Ham-A	X		X	X	X	X	X	
GNG/SST	X			X	X		X	
Vital Signs	X	X	X	X	X	X	X	
Labs, EKG	X		X			X		
UDS	X			X				
Dispense med		X	X		X	X		
Compliance			X	X	X	X		

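### The final safety visit (W14) may be done by mail, but the plan's only response to a report of suicidal thought is immediate and cannot be carried out on a mailed answer

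*Combined protocol and SAP*

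**What the plan says.** Four places in the combined protocol and SAP bear on this.

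- **C3. Method, Safety assessments.** "Anxiety, depression, and suicidal ideation will be assessed with Ham-A, Ham-D, and suicide screen in each of the visits". The same paragraph opens: "At each study visit, safety will be assessed by measuring: weight, sitting blood pressure, heart rate", and goes on to list adverse events (except at baseline) and concomitant medications.
- **C3. Method, Follow-up.** "The final visit, 30-days after study completion, will include safety assessments, along with follow-up of any unresolved adverse events". The paragraph ends: "This visit may be done over the phone or by mail". No condition is attached to either mode.
- **C3. Method, Suicide Screen.** If a subject reports suicidal thought at interview, the physician or psychiatrist is told and "the subject will be escorted to the ER immediately for further evaluation and treatment". No other response rule appears.
- **Table 1.** W14 is numbered as visit 8. CAARS-S:S, BAARS and Ham-D are marked there. The table has no row for the suicide screen.

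**The concern.** A suicide screen is useful only if someone can act on the answer. The plan sets the standard itself: the response is to be immediate. It then permits a mode of contact in which the answer may be days old when it is opened and the patient is not there to be helped. This goes beyond missing detail, because the plan expressly allows a route that its own safety rule cannot serve.

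The patients are veterans with PTSD and a CAPS score of at least 55, and depression secondary to PTSD is allowed. W14 is the last scheduled contact. For patients who take atomoxetine second (weeks 7-10), it is also the only one after the treatment period. What is at stake is a delayed response to a patient at risk. The estimate of the treatment effect is not at stake.

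**Working it through.** No sample-size, power or error-rate figure is involved. The check sets the texts side by side.

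**Step 1: is a safety contact due at W14?** The Follow-up paragraph calls it the final visit and says it includes safety assessments. The paragraph just before it, headed Safety assessments, places the suicide screen at every visit. Table 1 numbers W14 as visit 8 and marks Ham-D, one of the instruments named in the same sentence as the screen. The natural reading is that the screen is due.

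**Step 2: can the response rule work in each permitted mode?**

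| Mode at W14 | Inform physician or psychiatrist | Immediate emergency evaluation |
|---|---|---|
| In person | Yes | Yes, as written |
| Phone | Yes | Possible, but no procedure is given |
| Mail | Only once the letter is opened | No |

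**Step 3: how long is the gap before W14?** From W1 on, Table 1 places visits at W1, W2, W5, W6, W7, W10 and W14. The intervals are 1, 3, 1, 1, 3 and 4 weeks. The last (14 - 10 = 4 weeks, or 28 days, in line with the stated 30 days) is the longest, and it precedes the one visit that may be mailed.

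**Step 4: how far do Table 1 and the safety prose agree in general?** This bears on how much weight the blank cells at W14 can carry.

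| Item | Prose | Table 1 as it reads |
|---|---|---|
| Vital signs | Each study visit | Visits 1-7; blank at W14 |
| Adverse events | Each study visit except baseline | W2 and W7 only |
| Concomitant medications | Each study visit | Blank at W5, W10 and W14 |
| Ham-D | Each visit | Blank at W1; marked at W14 |
| Ham-A | Each visit | Blank at W1 and W14 |

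The mismatch runs through the schedule, so the blank vital-sign cell at W14 is one instance of loose drafting. It is not evidence of a specific decision about that visit.

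**The case against.** **W14 may not count as a visit.** C1. Overview says "Final follow up will be 30-days after last visit", which could put W14 outside any rule about each visit. That doubt is fair, and the Follow-up paragraph does not name the suicide screen. But it does call W14 a visit and requires safety assessments there. Even if the screen were not due, a Ham-D rating is, at a contact that may be mailed.

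**The response rule may be meant only for the initial interview.** It is worded for an interview. If so, the screens at all later visits have no response rule, and text is still needed.

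**The risk is small.** This stands. Mail is an option and not the default, active suicidal thoughts and behavior are excluded at entry, earlier visits are screened, and the Follow-up paragraph provides for continued clinic care.

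**Mail has a legitimate use.** This also stands. The CAARS-S:S is a self-report questionnaire due at W14, and A1 expects poorer attendance in patients with these symptoms. Removing mail altogether would go further than the problem requires.

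**A stronger reading that the documents do not support.** A reader might infer that patients who take atomoxetine second are left without cardiovascular monitoring, and might try to count those needing a recheck after W10. Vital signs are marked at W10 for everyone, an in-person final visit is not barred, unresolved adverse events are followed up, and hypertension is an exclusion. C2 also states: "Modest increases in heart rate and blood pressure were well tolerated and gradually decreased on cessation of treatment". The adult rates listed under 1.1 Risks to Subjects come with no cut-off or timing, so they cannot yield a number of rechecks. The rise of 15 to 20 mm Hg or 20 beats per minute listed under Contraindications concerns severe cardiac or vascular disorders. The plan does not offer it as a threshold for this healthier group.

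**Conclusion.** The point holds as a minor patient-safety matter. The plan requires safety assessments at W14, most naturally including a suicide screen, and allows a mode in which its only response rule cannot be followed.

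Its size cannot be put as an expected number of patients. The option is open at every final contact (40 completers planned, at most 50 enrolled), but the documents do not say how many contacts would be mailed. The only rate they give for suicidal thoughts under atomoxetine is pediatric (0.4%).

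The conclusion rests on two readings: that W14 is a visit for the purpose of the screen, and that a mailed answer cannot be acted on at once. The second is an inference, but a safe one. Nothing here touches the efficacy inference, since both treatment periods end by week 10. The mismatch between Table 1 and the prose is a secondary point of consistency only.

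**What to change.** 1. In the Follow-up paragraph, require the safety part of W14 (suicide screen, Ham-D, adverse events) to be done live, by phone or in person. Allow mail only for self-report forms such as the CAARS-S:S. A letter may ask a patient who cannot be reached to call, but should not carry the screen.
2. Add one sentence: if suicidal thought is reported by phone, the caller informs the physician or psychiatrist at once and arranges emergency evaluation before the call ends.
3. Secondary: align Table 1 with the safety prose. State whether vital signs are due at W14, and settle concomitant medications, adverse events, Ham-A and Ham-D at the visits listed above.

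The cost is a phone call in place of a letter, and possibly a few patients whose W14 safety part is missed because they cannot be reached live. No extra clinic visit is needed for items 1 and 2, which respects the plan's commitment to limit visits and time lost from work. Item 3 is wording, unless the sponsor decides that vital signs are due at W14, in which case that visit must be in person.
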